APPENDIX F: Brief Illness Perception Questionnaire (English)

Brief Illness Perception Questionnaire

For the following questions, please circle the number that best corresponds to your views:

How much does your illness affect your life?										
0 no affect at all	1	2	3	4	5	6	7	8	9	10 severely affects my life
How long do you think your illness will continue?										
0 a very short time	1	2	3	4	5	6	7	8	9	10 forever
How much control do you feel you have over your illness?										
0 absolutely no control	1	2	3	4	5	6	7	8	9	10 extreme amount of control
How much do you think your treatment can help your illness?										
0 not at all	1	2	3	4	5	6	7	8	9	10 extremely helpful
How much do you experience symptoms from your illness?										
0 no symptoms at all	1	2	3	4	5	6	7	8	9	10 many severe symptoms
How concerned are you about your illness?										
0 not at all concerned	1	2	3	4	5	6	7	8	9	10 extremely concerned
How well do you feel you understand your illness?										
0 don't understand at all	1	2	3	4	5	6	7	8	9	10 understand very clearly
How much does your illness affect you emotionally? (e.g. does it make you angry, scared, upset or depressed?)										
0 not at all affected emotionally	1	2	3	4	5	6	7	8	9	10 extremely affected emotionally

• All rights reserved. For permission to use the scale please contact: [contact]

Clinical Investigation Plan

APPENDIX G: Cardiac Health Security Survey

CARDIAC HEALTH SECURITY

We want to understand what it is like for you to live with a medical condition. Below are some statements that describe personal beliefs about your condition. Please rate the extent to which you agree or disagree with each of the following statements by checking the most appropriate box.

Strongly Disagree	Mostly Disagree	Neither Agree nor Agree	Mostly Agree	Strongly Agree
1	2	3	4	5

AVAILABILITY

- 1) I have the information that I need to be as healthy as possible.
- 2) I have the support that I need to be as healthy as possible.
- 3) I am not sure what to do to be healthy in the future.

ACTION

- 4) I don't know what symptoms of my condition that I should watch for.
- 5) I get mixed messages from different providers about what I need to do to take care of my health.
- 6) I don't know what to do if my condition worsens.

OUTCOME

- 7) If my health condition changes, I can get it back on track.
- 8) I can deal with my condition.
- 9) My condition is dangerous on a day-to-day basis.

FUTURE ORIENTATION

- 10) I look forward to better health in the future.
- 11) My health problems are not predictable.
- 12) It's hard to know when I will have "good days" or "bad days" as far as my health problems go.

WIHM SYSTEM EVALUATION AND IMPACT

- 13) Overall, I am satisfied with my pressure monitoring system.
- 14) Given the choice again, I would agree to get pressure monitoring system again.
- 15) The pressure monitoring system gives me a sense of control.
- 16) The pressure monitoring system provides me a sense of security.
- 17) My heart disease prevents me from planning activities in the future.
- 18) The pressure monitoring system provides my loved ones a sense of security.
- 19) The pressure monitoring system is a problem for me.
- 20) The pressure monitoring system was overwhelming to deal with.

This confidential document is the property of Abbott and shall not be reproduced, distributed, disclosed or used without the express written consent of Abbott

Clinical Investigation Plan

- 21) I lost interest in pressure monitoring.
- 22) I worry that my data is not secure.
- 23) The pros outweigh the cons for pressure monitoring.
- 24) I avoid making plans because I am afraid that I will not feel well enough to participate.

This confidential document is the property of Abbott and shall not be reproduced, distributed, disclosed or used without the express written consent of Abbott

Clinical Investigation Plan

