8.1. Screening Visit

During the screening visit, the following procedures/assessments will be performed to determine subject eligibility:

- Informed Consent prior to the conduct of any study-related procedures
- Physical examination including vital signs (temperature, heart rate, respiratory rate, blood pressure), weight, height, BMI calculation (refer to Appendix H)
- Medical and surgical history including ejection fraction data must be taken within the last 3 months to enroll in the study.
- Patient history of heart failure hospitalizations in the 12 months previous to the baseline visit as documented in information provided by the patient's cardiologist, internist, or referring physicians and review of all source documents of any heart failure hospitalization(s) reported in the previous year.
- Demographics

This confidential document is the property of Abbott and shall not be reproduced, distributed, disclosed or used without the express written consent of Abbott

Clinical Investigation Plan

- NYHA Functional Classification
- Calculation of GFR (requires creatinine - refer to Appendix I)
- Assessment of medications
- Kansas City Cardiomyopathy Questionnaire-12 (KCCQ-12) (refer to Appendix E)
- Brief Illness Perception Questionnaire (refer to Appendix F)
- Cardiac Health Security Survey (refer to Appendix G)
- Assessment of enrollment eligibility (inclusion/exclusion criteria)

The study coordinator or designee will administer patient-reported outcome questionnaires. It is important that the subject understands the meaning of all words and instructions in each questionnaire and answers all the questions. The subject will be instructed to ask any questions about the questionnaire if further explanation is needed. The research coordinator or designee will review the questionnaires to verify that all questions have been answered. The measures used will be the Kansas City Cardiomyopathy Questionnaire-12 (KCCQ-12), the Brief Illness Perception Questionnaire, and the Cardiac Health Security Survey. The Patient Reported Outcomes will be obtained at screening and each follow up visit post implant (with the exception of the 1 month follow-up visit) for 2 years. Patients who were enrolled in the study prior to addition of patient reported outcome questionnaires, and therefore did not complete baseline questionnaires, are not required to complete questionnaires at the follow-up visits.

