Eligible subjects will be scheduled for the Implant procedure. Subjects on anticoagulation therapy (e.g. warfarin) may be instructed by the Investigator to discontinue use 1-2 days prior to pressure sensor placement. The investigator should consider utilizing enoxaparin (Lovenox) per the site's standard of care as bridge therapy to Sensor placement in subjects who were on anticoagulation therapy.

For subjects at risk for gastro-intestinal bleeding during the period in which dual antiplatelet therapy is given, the investigator should consider a proton pump inhibitor such as omeprazole (Prilosec). Subjects at risk include the elderly, those with a history of gastroduodenal ulcers, gastroesophageal reflux disease, esophagitis, intestinal polyps or cancer. Subjects who smoke or who are using steroids or non-steroidal anti-inflammatory drugs may also be at risk.

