Patient improvement in Quality of Life will be reported. The difference between the Quality of Life scores at 6 months, 12 months, 18 months, and 24 months will be compared to the baseline values using general linear mixed models. Quality of Life will be measured using the Kansas City Cardiomyopathy Questionnaire-12 (KCCQ-12), the Brief Illness Perception Questionnaire, and the Cardiac Health Security Survey.

PAS SUB-STUDY

This section describes the design, hypotheses, populations, endpoints and analysis of the PAS sub-study. All other sections of the protocol pertain to the main PAS cohort unless specifically stated otherwise.

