APPENDIX B: Schedule of Events

	Screening	Baseline (Implant)	Month 1	Months 6 and every 6 Months thereafter until Study Termination
Procedures		(within 30 days of Screening)	Visit 1 (30 ± 7 days)	Visits 2-5 or Study Termination (± 30 day window)
Informed Consent	X			
Demographics	X			
Past Medical & Surgical History	X			
Inclusion/Exclusion Criteria Review	X	X		
GFR	X			
Kansas City Cardiomyopathy Questionnaire (KCCQ-12)	X			X
Brief Illness Perception Questionnaire	X			X
Cardiac Health Security Survey	X			X
INR (if indicated)		X		
Pulmonary artery measurement		X		
Physical Examination (including weight)	X ¹	X ²	X ²	X ²
NYHA HF Classification	X		X	X
Pulmonary Artery Angiography		X		
Sensor Implant		X		
Sensor Measurements		X	X (Investigator discretion)	X (Investigator discretion)
Adverse Events Assessment		X	X	X
Medication Assessment (heart failure)	X	X	X	X

¹ Includes weight, height and vital signs (temperature, blood pressure, pulse, respirations).

² Includes weight, vital signs and significant changes from previous physical examination

Clinical Investigation Plan

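### Nine or ten of the 24 Cardiac Health Security Survey items ask about a monitoring system the subject does not yet have at screening, yet Section 12.7.2 compares survey scores with that baseline and excludes no items

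*Combined protocol and SAP*

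**What the plan says.** Section 8.1 lists the survey among the screening procedures, "Cardiac Health Security Survey (refer to Appendix G"), with no instruction to leave any item out. The same section gives the timing: "The Patient Reported Outcomes will be obtained at screening and each follow up visit post implant", apart from the Month 1 visit. On completeness it says: "The research coordinator or designee will review the questionnaires to verify that all questions have been answered".

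Implantation comes later. Section 8.1 closes the screening step with "Eligible subjects will be scheduled for the Implant procedure", and Appendix B places the implant visit "within 30 days of Screening". Appendix B marks the survey at screening and from Month 6 onward, but not at the implant visit.

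Appendix G prints one form of 24 items under five headings, answered on a scale from 1 to 5. The last heading, on evaluation and impact of the monitoring system, covers items 13 to 24. Item 13 reads "Overall, I am satisfied with my pressure monitoring system".

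Section 12.7.2 (Quality of Life Evaluations) names this survey as one of three measures and says that scores at 6, 12, 18 and 24 months "will be compared to the baseline values using general linear mixed models".

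**The concern.** The only survey value before follow-up is taken when the subject has no sensor and has never used the system. Several items presuppose that experience: satisfaction with one's own system (13), whether one would choose it again (14), whether it was overwhelming (20), and whether one has lost interest in it (21). A screening answer to these is a guess or an expectation. A later change then compares expectation with experience, and that is not a change in quality of life.

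The stake is the meaning of the reported change for this survey. If device items enter the compared score, real change in the subject's sense of security cannot be separated from the move from imagining a device to using one.

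**Working it through.** The plan states no figure on this point, so there is none to reproduce. The check is an item count followed by a reading of what the analysis would do with those items.

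**1. Is the baseline taken before implant?** Yes. Section 8.1 and Appendix B put the survey at screening, and the implant follows. No survey is scheduled between implant and Month 6.

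**2. Which items concern the device?** (Appendix G)

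| Items | Content | Count |
|---|---|---|
| 1–12 | Information, symptoms, coping, outlook | 12 |
| 13, 14, 15, 16, 18, 19, 20, 21, 23 | Name pressure monitoring | 9 |
| 22 | Data security; device-related only by its place in the block | 1 |
| 17, 24 | Planning activities; no reference to the device | 2 |

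- Strict count: 9 / 24 = 37.5%, leaving 24 − 9 = 15 items with a usable baseline.
- Count with item 22: 9 + 1 = 10, and 10 / 24 = 41.7%, leaving 24 − 10 = 14 items.
- Within the last block alone: 9 / 12 = 75% to 10 / 12 = 83.3%.

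**3. Can a subject decline to answer?** The Appendix G scale has no option for an item that does not apply. The KCCQ-12 in Appendix E does offer one for its activity items. Section 8.1 asks staff to check that all questions are answered, and Section 12.3 has missing-data queries pursued with the site.

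**4. Does the analysis set these items aside?** Section 12.7.2 applies the baseline comparison to the survey without excluding any item, and no other section handles the device items separately. No section defines scoring, so there are two cases:

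- *Domain scores by printed heading.* Items 1–12 are untouched. The comparison for the last block rests on a baseline in which 9 or 10 of 12 items are unsound.
- *One total score.* The same items enter the whole score.

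**5. Can the artefact be sized?** No. Assume, for illustration only, a simple sum of all items. The total then spans 24 × 4 = 96 points, of which the device items carry 9 × 4 = 36 to 10 × 4 = 40. But six of the ten are worded favourably (13–16, 18, 23) and four unfavourably (19–22). If every device item moved one point towards a better view of the system, a raw sum would change by 6 − 4 = +2, while a sum with the unfavourable items reversed would change by 6 + 4 = +10. The plan states neither summation nor reversal, and nothing in it supports a shift of one point.

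**The case against.** The strongest case against is that Section 12.7.2 speaks only of scores and no score is defined. The five printed headings make domain scoring plausible, and then most of the instrument is unaffected. That stands: damage to the whole score is conditional. It does not remove the point, because the last block has an unsound baseline under either scoring.

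A second objection is that nobody is forced to answer. Section 16.1 has data fields completed where appropriate, and Section 12.3 leaves unresolved missing data unimputed. A reader might infer from the Section 8.1 check that the plan compels meaningless answers and requires them in the model. That goes too far: a completeness check is not an analysis rule, and the plan is silent on which items are analysed. Silence is still a gap. If some sites leave the items blank and others fill them in, baseline scores would rest on different item sets.

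Third, the count has soft edges. Item 22 does not mention the device and anyone could answer it. Item 23, on pros and cons, could be answered as an expectation by someone about to receive the sensor. Item 22 is why the count is given as a range. An expectation on item 23 is an answer, but not a baseline for later experience.

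Finally, the consequence is small. This is one of three questionnaires in a supplemental analysis with no stated success criterion. It does not appear in the Appendix L report tables, and under Section 8.1 subjects enrolled before the questionnaires were added need not complete it. All of that stands.

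**Conclusion.** The point holds as a defect in a supplemental analysis. Followed as written, the schedule and the baseline comparison give an uninterpretable change for the device items, which number 9 on a strict reading and 10 with item 22 (37.5% to 41.7% of the form). How far this spreads depends on scoring that the plan does not define: to one block under domain scores, to the whole score under a total.

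A reader might infer a specific bias, such as a 10-point shift in a total score. The documents do not support it. It needs an unweighted sum, reverse scoring and a uniform one-point shift, none of which is stated. No primary endpoint, sample size or error rate is touched.

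**What to change.** In Section 12.7.2:

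- State how the survey is scored, including any reversal of unfavourably worded items.
- Limit its change-from-baseline mixed model to items that can be answered before implant: items 1–12, with items 17 and 24 either included, if the stated scoring allows, or reported separately.
- Exclude any screening answers to items 13–16 and 18–23, and summarise those items descriptively at follow-up visits only.

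Add a case report form instruction to skip those items at screening only if enrollment is still open. Version C is dated 19 February 2018 and Appendix A anticipated complete enrollment in December 2017. If that timeline held, the analysis rule is the useful part.

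The cost is a few sentences of analysis wording and no new data. The downside is a shorter baseline-comparable score: 12 items, or 14 with items 17 and 24, in place of 24.

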APPENDIX H: BMI Calculator

To calculate subjects Body Mass Index using the website below:

<http://www.nhlbisupport.com/bmi/bmi-m.htm>

Enter the subjects Weight and Height and then calculate BMI (print screen for source documentation)

Formulas used to calculate Body Mass Index:

English BMI Formula

BMI = Weight in pounds/ (height in inches x height in inches) x 703

Metric BMI Formula

BMI = Weight in kilograms/ (height in meters x height in meters)

Note that BMI may also be calculated within the eCRF.

This confidential document is the property of Abbott and shall not be reproduced, distributed, disclosed or used without the express written consent of Abbott

Clinical Investigation Plan

APPENDIX I: Glomerular Filtration Rate

To calculate subjects Glomerular Filtration Rate use the website below:

<http://www.nephron.com/cgi-bin/CGSI.cgi>

Enter the subjects Creatinine level, Age, Race, Gender then calculate (print screen for source documentation)

GFR (mL/min/1.73 m²) = 186 x (S_{cr})^{-1.154} x (Age)^{-0.203} x (0.742 if female) x (1.210 if African American)

Note that GFR may also be calculated within the eCRF.

This confidential document is the property of Abbott and shall not be reproduced, distributed, disclosed or used without the express written consent of Abbott

Clinical Investigation Plan

APPENDIX J: Protocol Definitions

Enrollment – After meeting study inclusion criteria and following successful Sensor implant, subjects are considered enrolled

Hospitalization – Greater than or equal to 24 hours in a hospital

HF Hospitalization – hospitalization determined to be related to heart failure as determined by the CEC

Active Infection – Febrile, elevated WBC, left shift, on antibiotics, positive cultures (blood, sputum or urine)

PI – Appropriate clinician designated as the Principal Investigator on the “Investigator Agreement” received and approved by St. Jude Medical. For study related procedures/visits PI refers to the PI or his/her designee.

Source documents – Primary study documentation including electronic, paper, phone messages, etc. containing study-pertinent information such as visit information, clinical history, medications, (S)AE reporting, etc. These documents are originals and should be treated as such. Information from these documents will be transferred from and compared against information reported in study CRFs

Sub-investigator – Clinical personnel designated as a sub-investigator on the “Investigator Agreement” received and approved by St. Jude Medical

Worksheets –Source documents used for calculation of clinical values such as BMI or EGFR from screening to end of study. Worksheets may also be used during the sensor implant or follow-up visits to capture information not captured in the medical record. In order for these worksheets to be considered valid, the Investigator must sign and date the worksheet.

This confidential document is the property of Abbott and shall not be reproduced, distributed, disclosed or used without the express written consent of Abbott

Clinical Investigation Plan

APPENDIX K: Composition, Function, and Procedures of the Clinical Events Committee (CEC)

The hospitalizations and deaths in this study will be monitored by a Clinical Events Committee (CEC). The committee will be comprised of physicians, who will not participate in the enrollment or treatment of subjects in this trial. The CEC members have agreed with the study design and protocol. CEC members are independent and cannot be removed based on difference of opinion on study-related matters with St. Jude Medical, Investigators, or any St. Jude Medical contractor.

The members of the CEC are responsible for reviewing the safety data and providing an assessment of the data according to their individual expertise. The CEC Committee will evaluate all SAEs to determine whether or not the SAE is device / system-related. The interpretation of events as classified and adjudicated by the clinical events committee will be used in the final effectiveness and safety analyses.

The role and procedures of the CEC Committee will be detailed in the CEC charter.

[figure not shown]
This confidential document is the property of Abbott and shall not be reproduced, distributed, disclosed or used without the express written consent of Abbott

Clinical Investigation Plan

APPENDIX L: Reporting of Interim Analyses

Updates from the PAS will be submitted to FDA as a PMA supplement every 6 months for the first two years of the study (annually thereafter). This information will include the following information:

Study enrollment and follow-up status

This confidential document is the property of Abbott and shall not be reproduced, distributed, disclosed or used without the express written consent of Abbott

Clinical Investigation Plan

Demographic information

	Premarket Study	PAS Aggregate	PAS Male	PAS Female
Average Age (years)	XX.X ± XX.X	XX.X ± XX.X	XX.X ± XX.X	XX.X ± XX.X
Male	XX.X%	XX.X%	XX.X%	XX.X%
Caucasian	XX.X%	XX.X%	XX.X%	XX.X%
Average BMI	XX.X ± XX.X	XX.X ± XX.X	XX.X ± XX.X	XX.X ± XX.X
Average LVEF	XX.X ± XX.X%	XX.X ± XX.X%	XX.X ± XX.X%	XX.X ± XX.X%
LVEF < 40%	XX.X%	XX.X%	XX.X%	XX.X%
Ischemic Cardiomyopathy	XX.X%	XX.X%	XX.X%	XX.X%
Average PA Systolic (mmHg)	XX.X ± XX.X	XX.X ± XX.X	XX.X ± XX.X	XX.X ± XX.X
Average PA Diastolic (mmHg)	XX.X ± XX.X	XX.X ± XX.X	XX.X ± XX.X	XX.X ± XX.X
Average PA Mean (mmHg)	XX.X ± XX.X	XX.X ± XX.X	XX.X ± XX.X	XX.X ± XX.X
Average PA Wedge (mmHg)	XX.X ± XX.X	XX.X ± XX.X	XX.X ± XX.X	XX.X ± XX.X
Average Cardiac Output (L/min)	XX.X ± XX.X	XX.X ± XX.X	XX.X ± XX.X	XX.X ± XX.X
Average Cardiac Index (L/min/m ²)	XX.X ± XX.X	XX.X ± XX.X	XX.X ± XX.X	XX.X ± XX.X

Safety

	6 Months N=XXXX		12 Months N=XXXX		18 Months N=XXXX		24 Months N=XXXX	
	N	Percent	N	Percent	N	Percent	N	Percent
DSRCs	XXX	XX.X%	XXX	XX.X%	XXX	XX.X%	XXX	XX.X%
Pressure Sensor Failures	XXX	XX.X%	XXX	XX.X%	XXX	XX.X%	XXX	XX.X%

Heart Failure Hospitalizations

	6 Months N=XXXX	12 Months N=XXXX	18 Months N=XXXX	24 Months N=XXXX
HF Hospitalizations	XXX	XXX	XXX	XXX
HF Hospitalization Rate:				
Events/patient years	X.XX	X.XX	X.XX	X.XX
Events/patient days	X.XX	X.XX	X.XX	X.XX
HF Hospitalization Proportion	XX.X%	XX.X%	XX.X%	XX.X%

Mortality

	6 Months N=XXXX		12 Months N=XXXX		18 Months N=XXXX		24 Months N=XXXX	
	Deaths	Percent	Deaths	Percent	Deaths	Percent	Deaths	Percent
All Cause Deaths	XXX	XX.X%	XXX	XX.X%	XXX	XX.X%	XXX	XX.X%
Cardiac Deaths	XXX	XX.X%	XXX	XX.X%	XXX	XX.X%	XXX	XX.X%
Non-Cardiac Deaths	XXX	XX.X%	XXX	XX.X%	XXX	XX.X%	XXX	XX.X%

This confidential document is the property of Abbott and shall not be reproduced, distributed, disclosed or used without the express written consent of Abbott

Clinical Investigation Plan

Serious Adverse Events

	6 Months N=XXXX		12 Months N=XXXX		18 Months N=XXXX		24 Months N=XXXX	
	Subjects	Events	Subjects	Events	Subjects	Events	Subjects	Events
All Patients with an Event	XX (XX.X%)	XXX	XX (XX.X%)	XXX	XX (XX.X%)	XXX	XX (XX.X%)	XXX
System Organ Class I	XXX	XXX	XXX	XXX	XXX	XXX	XXX	XXX
...								

Days alive outside of hospital for heart failure

	6 Months N=XXXX	12 Months N=XXXX	18 Months N=XXXX	24 Months N=XXXX
	N	N	N	N
Days Alive outside of Hospital	XXX	XXX	XXX	XXX

Weekly Patient Pressure Reading Compliance

	Compliance %
Mean \pm StdDev	XX.X \pm XX.X%
Median	XX.X%

Sensor Performance

	N	Percent
Number of Patients	XXX	XX.X%
Number of RHCs with comparative readings	XXX	XX.X%

Results will be presented using Bland-Altman comparing Sensor vs. Swan-Ganz.

Clinical Investigation Plan

[figure not shown]
Medication changes in response to PA pressure

Medication Changes in Response to PA Pressure	# Medications	
	N	Percent
ACE/ARB	XXX	XX.X%
Aldosterone Antagonist	XXX	XX.X%
Beta-blocker	XXX	XX.X%
Diuretic-Loop	XXX	XX.X%
Diuretic-Thiazide	XXX	XX.X%
Hydralazine	XXX	XX.X%
Nitrate	XXX	XX.X%
Other	XXX	XX.X%
Total	XXX	XX.X%

This confidential document is the property of Abbott and shall not be reproduced, distributed, disclosed or used without the express written consent of Abbott

Clinical Investigation Plan

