12.7.2. Supplemental Analyses

Mortality

The mortality rate over 1 year in study will be reported. Plotting and analysis of survival data will be displayed using Kaplan-Meier methods.

HF Hospitalization or Death

The annualized HF hospitalization or death rate parameter, λ , at 1 year will be compared to the HF hospitalization rate in the year prior to enrollment using a two-sample, two-sided Poisson confidence interval. If the two-sided, upper 95% confidence interval for the PAS rate parameter is less than that in the year prior to enrollment, then the hypothesis will be met.

Mathematically stated, the hypothesis is:

$$H_0: \lambda_{(12 \text{ month HF Hospitalization or Death Rate})} \geq \lambda_{(\text{HF hospitalization rate in year prior to enrollment})}$$

$$H_a: \lambda_{(12 \text{ month HF Hospitalization or Death Rate})} < \lambda_{(\text{HF hospitalization rate in year prior to enrollment})}$$

where $\lambda_{(12 \text{ month HF Hospitalization or Death Rate})}$ = the HF hospitalization or death rate parameter at 1 year in the PAS and $\lambda_{(\text{HF hospitalization rate in year prior to enrollment})}$ = the HF hospitalization rate in the year prior to enrollment.

Patient Compliance

Patient device usage over the course of the trial will be examined. The total number of PA pressure readings taken will be reported as a percentage of patient days at home.

This confidential document is the property of Abbott and shall not be reproduced, distributed, disclosed or used without the express written consent of Abbott

Clinical Investigation Plan

Training Evaluation

To assess the effectiveness of the training program, the safety and effectiveness results will be reported for:

- 1) Academic Hospitals
- 2) Community Hospitals

Subgroup Analyses

The effectiveness analyses will be evaluated in each of the following subgroups:

- 1) Women
- 2) Men
- 3) Reduced Ejection Fraction (< 40%)
- 4) Preserved Ejection Fraction ($\geq 40\%$)
- 5) Ischemic Etiology
- 6) Non-ischemic Etiology
- 7) With ICD/CRT-D
- 8) Without ICD/CRT-D

Quality of Life Evaluations

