13.9.3. Schematic Diagram of the Sub-study and Main PAS Study

See Appendix M for a schematic diagram of the Main PAS Study and the PAS Sub-study.

REPORTING OF INTERIM AND PRIMARY ANALYSES

In addition to the primary safety and effectiveness analyses, updates from the PAS will be submitted to FDA as a PMA supplement every 6 months for the first two years of the study (annually thereafter) and updated in the device labeling. This information will include the following: study enrollment and follow-up status; demographic information; safety and effectiveness results; mortality; serious adverse events; days alive outside of the hospital for heart failure; patient compliance; sensor performance; and medication changes in response to PA pressure. Please refer to Appendix L: Reporting of Interim Analyses.

The primary safety analyses will be reported after all patients complete 24 months post enrollment or discontinue early. The primary effectiveness analyses will be reported after all patients complete 12 months post enrollment or discontinue early.

CLINICAL EVENTS COMMITTEE

An independent clinical events committee (CEC) will be formed to review clinical data. The committee will be comprised of physicians, who will not participate in the enrollment or treatment of subjects in this trial. All endpoints or suspected endpoints will be reviewed by this committee according to the CEC Committee charter. Any event listed in the CEC Committee charter reported in an SAE report or the CRF will trigger the accumulation of a portfolio of pertinent documents from the hospital admission. These documents will be collected and copies distributed to members of the CEC Committee. The

This confidential document is the property of Abbott and shall not be reproduced, distributed, disclosed or used without the express written consent of Abbott

Clinical Investigation Plan

interpretation of the event as classified and adjudicated by the clinical events committee will be used in the final effectiveness and safety analyses.

The composition and function of the CEC Committee is described in Appendix K.

DATA COLLECTION, STUDY MONITORING, AND DATA DISCLOSURE

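### Appendix L reports complications, sensor failures, deaths and the HF hospitalization proportion as crude percents over an undefined N, without the Kaplan-Meier methods the plan names elsewhere

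*Combined protocol and SAP*

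**What the plan says.** Appendix L sets the content of the periodic updates: "Updates from the PAS will be submitted to FDA as a PMA supplement every 6 months for the first two years of the study", and yearly after that. Section 14 repeats the schedule and says the information is also "updated in the device labeling".

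The outcome tables in Appendix L have four columns, each with its own denominator, for example "6 Months N=XXXX" and "12 Months N=XXXX". Nothing in Appendix L or section 14 says whether N is everyone enrolled, those who could have reached that month, or those who did.

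Under these columns:

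- The Safety table gives a count and a percent for complications and for "Pressure Sensor Failures".
- The Mortality table gives deaths and a percent for "All Cause Deaths", with cardiac and non-cardiac rows below.
- The HF hospitalization table gives a crude proportion, and also events per patient-year and per patient-day.

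These tables contain no number at risk, confidence interval, censoring rule or Kaplan-Meier estimate.

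Elsewhere the plan does name a censoring-based method. Section 12.7.2 says of mortality: "Plotting and analysis of survival data will be displayed using Kaplan-Meier methods". Section 12.6.1 says the same of the primary safety endpoints. Neither says whether those displays belong in the updates.

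**The concern.** Appendix A spreads enrollment over 37 study months, so updates fall due while many subjects have not reached the later columns. A crude percent then mixes complete and incomplete follow-up, and what it estimates depends on the unstated N. If N is all enrolled, recent subjects count in full but have had little time for an event, so the percent is too low. If N is those who reached the month or had the event, early events from recent subjects enter both numerator and denominator while their event-free peers are left out, so it is too high.

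At stake are figures sent to FDA and used to update the labeling. They could move between updates because follow-up matures or the denominator is read differently, not because the device performs differently.

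**Working it through.** There is no stated figure to reproduce, because the Appendix L tables are empty shells. The check shows what the 24-month death cell would contain under each reading of N.

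**Inputs from the documents**
- Appendix A, with December 2014 as study month 1: 696 enrolled by December 2016 (month 25) and 1200 by December 2017 (month 37), so (1200 − 696)/12 = 42 per month in the last year.
- Section 12.2: two-year attrition of 49.1%, stated for CHAMPION. The counts printed beside it, 228/550, give 41.5%.
- Synopsis: version C is dated 19 February 2018. The illustration therefore uses a later cut-off, the end of December 2018 (month 49).

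**Assumptions, not in the documents**
- 12-month mortality of 15% (10% as a second case), constant hazard, entry at mid-month.
- Independent dropout of 0%, 30% or 49.1% over 24 months. The last is an upper bound, since attrition may include deaths.

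**True risk.** The hazard is h = −ln(0.85)/12 = 0.01354 per month. The 24-month risk is 1 − 0.85² = 27.8%.

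**No dropout, 24-month cell**
- The 696 subjects enrolled by December 2016 have all had 24 months: 696 × 0.2775 = 193.1 expected deaths, and 696 × 0.7225 = 502.9 survivors to month 24.
- The other 504 have 12.5, 13.5, …, 23.5 months of follow-up, 42 subjects at each. Expected deaths are 42 × Σ[1 − exp(−h f)] = 108.6.
- Total deaths: 193.1 + 108.6 = 301.7.
- N = all enrolled: 301.7/1200 = **25.1%**.
- N = died or reached month 24: 301.7/(301.7 + 502.9) = **37.5%**.
- N = enrolled at least 24 months earlier, counting only their deaths: 193.1/696 = **27.8%**, which is unbiased.

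**With dropout, N = enrolled at least 24 months earlier.** With dropout hazard d, the expected percent is h/(h + d) × [1 − exp(−24(h + d))].
- 30% dropout: d = −ln(0.70)/24 = 0.01486. The result is 0.4768 × (1 − 0.7225 × 0.70) = **23.6%**.
- 49.1% dropout: d = −ln(0.509)/24 = 0.02814. The result is 0.3249 × (1 − 0.7225 × 0.509) = **20.5%**.

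Once follow-up ends, everyone has had 24 months of opportunity, so the all-enrolled percent takes these same values. The shortfall does not go away. Kaplan-Meier targets 27.8% in every case, given independent censoring.

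**12-month column at the same date.** The last subjects entered in December 2017, so all 1200 have had 12 months. With no dropout the cell reads 15.0% under all three readings.

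**Second case, 10% 12-month mortality.** The true 24-month risk is 1 − 0.90² = 19.0%, and h = 0.00878. Deaths are 132.2 + 73.5 = 205.7. The cell reads 205.7/1200 = 17.1%, or 205.7/(205.7 + 563.8) = 26.7%. The restricted denominator reads 0.3714 × (1 − 0.81 × 0.70) = 16.1% with 30% dropout, and 0.2378 × (1 − 0.81 × 0.509) = 14.0% with 49.1%.

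**The case against.** The best defence is that a separate N per column suggests a time-specific denominator. If N means subjects enrolled long enough ago, counting only their events, staggered entry causes no bias, as shown above. This stands, but the plan does not choose that reading, and it still reads low when subjects withdraw.

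The plan also mitigates in part. HF hospitalization has exposure-adjusted rates alongside the proportion. Each update includes enrollment and follow-up status, whose layout is not visible in the text, so its content cannot be judged. No hypothesis test uses these tables, and the primary analyses wait for all subjects to finish or leave.

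A reader might infer several stronger things that the documents do not support:

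- *That Kaplan-Meier is reserved for the final analyses.* Sections 12.6.1 and 12.7.2 set no such limit. The gap is that Appendix L does not carry the method over.
- *That the percents are necessarily wrong until follow-up ends.* The error depends on N. On planned accrual the 12-month column is free of staggered-entry bias by December 2018, whereas the effect of withdrawal outlasts follow-up.
- *That the much larger gaps computable for 2016 and 2017 can still be corrected.* Those dates precede version C.
- *That complications are understated as much as deaths.* The illustration assumes a constant hazard. Complications clustered around implant would be understated less.
- *That the performance-criterion conclusions are at risk.* These tables do not feed them.

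**Conclusion.** The point holds as a reporting weakness in Appendix L. The percents rest on an undefined N, the tables omit a method the plan already accepts, and the figures go to FDA and the labeling. Under the assumptions above, the December 2018 24-month death cell could read anywhere from 25.1% to 37.5% against 27.8% with no dropout. Even the most defensible denominator falls short by about 4 to 7 percentage points with 30% to 49.1% dropout (27.8 − 23.6 = 4.2; 27.8 − 20.5 = 7.3). The direction of each error does not depend on the assumed mortality, but the size does. It also depends on actual accrual matching Appendix A and on dropout being independent of risk. Defining N alone would not be enough, because no simple denominator handles withdrawal.

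**What to change.** In the Appendix L Safety, Mortality and HF hospitalization tables:

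- Keep the event counts, and define N in each column as the number at risk at that month.
- Replace the percent for all-cause death with a Kaplan-Meier estimate.
- Replace the percents for complications, sensor failure and first HF hospitalization with cumulative incidence estimates, treating death as a competing event. A death that itself meets the complication definition in 9.1.1 counts as the event.
- Use cumulative incidence for cardiac and non-cardiac death, each competing with the other. Plain Kaplan-Meier would overstate both.
- Give 95% intervals, and censor at the last contact at which events were assessed.
- Leave the event-rate rows as they are.
- State in section 14 that these estimates are the ones used for the labeling.

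The cost is a change of table shells and programming. No new data are needed, and no hypothesis, sample size or test changes. The drawback is wide intervals or empty cells at late months in early updates.
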